These variables were chosen keeping in mind the most frequently cited risk factors for development of bipolar disorder in previous longitudinal studies of major depression

At least one of the following:

1. Family history of bipolar disorder in at least one first degree relative
2. History of any sub-threshold hypomania symptoms
3. History of mood episode related psychotic symptoms

Additional Inclusion criteria for Low Risk UD (LRUD) patients beside the inclusion criteria for UD:

These variables were chosen to minimize any overlap between the HRUD and LRUD groups.

1. No family history of BD in a first or a second degree relative
2. No past history of any sub-threshold hypomania symptoms
3. No history of psychotic symptoms

Exclusion criteria for UD and BDD patients:

1. Meeting DSM-IV criteria for schizophrenia, schizophreniform disorder, schizoaffective disorder, mental retardation, pervasive developmental disorder.
2. History of receiving electroconvulsive therapy in the past 1 year
3. Use of neuroleptics, mood stabilizers or benzodiazepines in the past 2 weeks.
4. Use of antidepressants in the past 2 weeks.
5. If on fluoxetine in the past, then should not have been on this medication for 5 weeks.
6. Acutely suicidal or homicidal or requiring inpatient treatment.
7. Meeting DSM-IV criteria for other substance/alcohol dependence within the past 6 months or abuse in the past 3 months, excluding caffeine or nicotine. The criteria will be evaluated by interview and urinary toxicology screening. The use of caffeine or nicotine will be recorded.
8. Use of alcohol in the past 1 week before the MRI scan.
9. No serious acute or chronic medical or neurological illness, including previously known HIV positive status (due to possible CNS involvement) as assessed by history, physical examination and laboratory examination including EKG, CBC and blood chemistry.
10. Current pregnancy or breast feeding.
11. Metallic implants or other contraindication to MRI.

Inclusion criteria for healthy subjects: Healthy subjects matched for age, gender and ethnicity will be included

1. Ages 15 - 30 years (inclusive) and able to give voluntary informed consent (consent will be taken from both parents and child for children under the age of 18)

2. No current or past history of psychiatric illness or substance abuse or dependence.
3. No current or past history of psychiatric illness or substance abuse or dependence in a first degree relative.

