Exclusion criteria for healthy subjects:

1. Pregnant or breast feeding.
2. Metallic implants or other contraindication to MRI.
3. Significant family history of psychiatric or neurological illness.
4. Currently taking any prescription or centrally acting medications.
5. Serious acute or chronic medical or neurological illness as assessed by history, physical examination and laboratory examination including CBC and blood chemistry.
6. Use of alcohol in the past 1 week and not being able to avoid alcohol use during the course of the study.

E 1b. Potential Risks:

Risks associated with this study are those associated with the interview for psychiatric symptoms, venous blood drawing, MRI scan, potential delay in treatment, antidepressant treatment for UD patients, emergence of mania or hypomania, and loss of confidentiality.

E1b1. Interview for psychiatric symptoms: Some patients may become anxious when they focus on their symptoms.

E1b2 . Venous blood drawing for blood tests during screening: This can lead to pain and bruising at site. In rare cases inflammation or infection of the site can occur.

E1b3. MRI scan: There are almost no known significant physical risks associated with MRI. The only exceptions are individuals with certain surgical implants such as cardiac pacemakers. Subjects with such implants will be excluded from any study. A screening procedure will be used identical to that used for clinical MRI scanning. Subjects not passing the screening will be excluded from the study as being contraindicated for MRI. Subjects will be fully informed about the fMRI procedures with a written consent form. We will also show them pictures of the MRI machine and the visual apparatus so that they are fully aware of the procedures involved. Patients reporting previous experience of anxiety in closed spaces will be excluded.

E1b4. Delay in treatment: patients will only be included in the study if they are unmedicated at the time of initial screening. We will not do a medication wash-out for the purpose of this study. However, patients need to be kept off medication between screening and time of the scan. This may delay their treatment for a few weeks and worsen their depression. Patients may become suicidal or significantly impaired in terms of their functioning.

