E2b4. Delay in treatment: Patients will only be included in the study if they are not on any psychotropic medications for at least 2 weeks at the time of the study. Therefore, there is no medications washout for the purposes of this study. Patients will undergo baseline ratings and MRI scans as soon as possible once they have been deemed to be eligible and have signed the consent form. From our experience of conducting the preliminary study we are usually able to arrange the baseline scan within a week once the patient is found to be eligible for the study and signs the consent form. Even in clinical settings, an evaluation period of 7 – 10 days is not uncommon before mild to moderately ill outpatients are started on medication. Subjects will be clinically assessed according to the criteria noted above, including lack of any significant suicidal or homicidal ideation and 17-item HAM-D score < 25, YMRS score < 10 and CGI severity score < 5 i.e., subjects will be judged to be only moderately ill. Patients will also be assessed regarding whether they can tolerate to continue as outpatients while not being on medications for 7 – 10 days. If not, then subjects will not be included in the study and either started on treatment at Indiana University Hospital or referred to the clinician of their choice. It is expected that most of the patients identified by the inclusion and exclusion criteria will be moderately ill depressed outpatients and they will not need inpatient treatment. However, once the patient is included in the study and their condition worsens, an option is available for them to be admitted into an inpatient research unit and treated clinically as described below. The P.I. has been conducting imaging studies with this category of patients for past 15 years and has considerable experience in safely getting patients through these studies.

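### The control alcohol exclusion is a joint condition with no link to the scan date, so a healthy control may be scanned within a week of drinking when no patient may

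*Combined protocol and SAP*

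**What the plan says.** All the eligibility rules are in section 3 (Human Subjects) of the combined protocol and SAP.

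- **Alcohol, patients** (E1a, exclusions for UD and BDD, no. 8): "Use of alcohol in the past 1 week before the MRI scan". There is no second condition.
- **Alcohol, controls** (E1a, exclusions for healthy subjects, no. 6): "Use of alcohol in the past 1 week and not being able to avoid alcohol use during the course of the study". Two conditions are joined by *and*, and the week is not tied to the scan.
- **Drugs, patients** (E1a, nos. 3 to 5): "Use of neuroleptics, mood stabilizers or benzodiazepines in the past 2 weeks"; "Use of antidepressants in the past 2 weeks"; and "If on fluoxetine in the past, then should not have been on this medication for 5 weeks". E2b4 describes the same patients more broadly, as "not on any psychotropic medications for at least 2 weeks at the time of the study".

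Section 2c(ii)E puts screening at Visit 1 and the scan at Visit 2. E2b4 says a patient's scan can usually be arranged within a week of eligibility and consent. No interval is given for controls.

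**The concern.** The controls are the reference group for illness effects. Hypothesis 1 sets BDD against both UD and controls on resting connectivity, and UD against both BDD and controls on dorsal ACC activation. The Aim 2 analysis is a one-way ANOVA that includes controls as one of four groups. If the entry rules allow recent drinking in controls but not in patients, recent alcohol use becomes associated with diagnosis by design. Part of a patient-control difference, or part of its absence, could then reflect alcohol rather than illness. The controls are matched on age, gender and ethnicity, none of which deals with drinking in the days before a scan.

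**Working it through.** No sample size, power or alpha figure is involved, so this is a check of logic and timing.

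**1. Who is excluded.** Treat the two weeks as the same week for the moment.

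| Drank in the week | Cannot abstain during study | Patient, no. 8 | Control, no. 6 as written | Control, no. 6 read as two separate exclusions |
|---|---|---|---|---|
| yes | no | excluded | **eligible** | excluded |
| yes | yes | excluded | excluded | excluded |
| no | yes | eligible | eligible | excluded |
| no | no | eligible | eligible | eligible |

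As written, the rules differ in the first row only. The control exclusion is a subset of the patient exclusion.

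**2. What the missing scan anchor does.** Let *s* be the days from last drink to screening and *d* the days from screening to scan. Suppose the control abstains from screening onward. At the scan the last drink was *s + d* days ago.

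- The patient rule excludes when *s + d* < 7.
- The control rule as written puts no limit on *s + d*.
- For a drink the day before screening, *s* = 1, so the gap is open whenever *d* < 6.
- If *d* is 7 or more, the gap is closed for any control who does abstain.

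The patient timetable in E2b4 makes *d* of about a week or less the usual case. That controls are scanned on a similar timetable is an assumption. Section 2c(ii)E allows scans to slip, which lengthens *d* and narrows the gap.

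**3. If *and* was meant to list two separate exclusions.** With the week counted back from screening, an eligible control has *s* of at least 7, so *s + d* is at least 7 provided abstention is kept. The literal gap closes. Two differences remain: no. 6 still gives no scan-day check, and controls face an abstention condition over an undefined study course (they may opt for 24 months of phone follow-up) that patients do not face.

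**4. Whether the analysis repairs it.** The covariate paragraph in the Statistical Analysis section names substance abuse. E1a adjusts for history of alcohol and substance abuse. Neither names alcohol in the days before the scan. Neither the Visit 2 description nor Table 3, as far as the table can be read, lists a pre-scan alcohol check.

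**5. Which contrasts are exposed.** BDD, HRUD and LRUD (40, 60 and 60 subjects) share exclusion no. 8. Only the 40 controls fall under no. 6. The Aim 1 ANOVA is specified for BDD and UD and is powered on that contrast, so it is unaffected. The control comparisons in Hypothesis 1 and the Aim 2 four-group ANOVA are exposed.

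**6. Drug wording.** Nos. 3 to 5 name four classes (neuroleptics, mood stabilizers, benzodiazepines, antidepressants), with a longer window for fluoxetine. E2b4 covers every psychotropic for at least 2 weeks. One patient can satisfy both, but the numbered list is narrower than the description.

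**The case against.** The strongest reply is that no. 6 does restrain drinking. A control who drank in the past week is eligible only if able to avoid alcohol during the study, and the scan is part of the study. This stands. A reader might infer that controls may drink freely up to the night before the scan; the text does not support that. It also rules out multiplying the 40 controls by an assumed weekly drinking rate, because that treats enrolled controls as if they went on drinking as usual. What is left is drinking shortly before screening followed by a scan inside seven days.

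A second reply is that *and* is loose drafting. That is plausible, since the literal text admits someone who cannot abstain but happened not to drink last week. It weakens the point but leaves a criterion that can be applied in two ways and has no scan anchor.

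A reader might also infer a mismatch running both ways. For alcohol on the literal text it does not, as the table shows.

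On drugs, a reader might infer that patients on unlisted psychotropics will be enrolled. E1b4 requires patients to be unmedicated at initial screening and to stay off medication until the scan, and E2b4 points the same way, so most of that gap is closed. Controls are barred only if "Currently taking any prescription or centrally acting medications", with no look-back, but they may have no current or past psychiatric illness, so recent psychotropic use among them is mostly a theoretical possibility. Nothing here argues for relaxing their prescription bar.

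**Conclusion.** The alcohol criteria for patients and controls are not equivalent. As written, a control may be scanned less than a week after drinking, which would exclude any patient. This rests on three assumptions: the *and* is applied literally, the control abstains from screening onward, and the interval from screening to scan is short enough that *s + d* is below 7.

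The size of any bias cannot be given. The documents contain no drinking rate and no effect of recent alcohol on connectivity or activation. It would be too strong to say that patient-control differences cannot be attributed to illness; the supported statement is that an avoidable confounder has been left in those contrasts. The comparisons among patient groups stand. Severity is minor.

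The drug wording is a secondary matter of consistency between the numbered patient criteria and E2b4.

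**What to change.** 1. Replace control exclusion no. 6 with the rule patients already have, "Use of alcohol in the past 1 week before the MRI scan", and remove inability to abstain as a joint condition. If the sponsor wants an abstention requirement, list it as its own criterion and state the period it covers.
2. Reconcile patient exclusions nos. 3 to 5 with E2b4 so that the numbered criteria and the description have the same scope. The choice of scope is the sponsor's.

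The cost is one amendment to eligibility wording. Controls would be asked at the scan visit about the past week, as the patient rule already requires for patients, and a few control scans would be rescheduled. Sample size and analysis do not change.

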ii. Screening Items list for Manic Syndrome From the Schedule for Affective Disorders and Schizophrenia (MSC-SADS)³: consists of five items that can be rated on a scale of 1- 6 with a possible score of 5 – 30. SADS a precursor of DSM diagnostic criteria has been shown to have high reliability and validity³. Pertinent to current proposal, the MSC-SADS uses a score rather than a dichotomous measure of presence of absence of (hypo)mania. We decided to include the MSC-SADS in addition to the YMRS because this screening questionnaire has been very recently reported to be able to screen for bipolarity in patients with unipolar depression and predict the development of (hypo)mania¹. [name] the primary author of the study has agreed to be a consultant for this proposal.

- iii. **Clinical Global Impressions of Severity Scale-Bipolar Version (CGI-BP)**⁷⁸. The CGI-BP is a modified version of the original CGI designed specifically for use in assessing global illness severity and/or change in patients with bipolar disorder and assesses overall bipolar illness, depression, and mania.
- iv. **17-item Hamilton Depression Scale**⁷⁹ and **Hamilton Anxiety Scales**⁸⁰: are gold standards for assessing symptom severity of depression and anxiety respectively.
- v. **Life events scale**⁸¹ and **childhood events scales** would be used to document events which could contribute to development of depression. Scores would be used as covariates in the analysis.
- vi. **Treatment Emergent Side Effect Scale (TESES)**
- vii. **Columbia Suicide Severity Rating Scale (CSSRS)** Scale used for identifying the presence and severity of suicide ideation.
- viii. **Beck Scale for Suicide Ideation (BSSI)** Scale used for identifying the presence and severity of suicide ideation.
- ix. **Structured Clinical Interview for DSM-IV Personality Disorders (SCID-II)** Scale used for identifying the presences of DSM-IV personality disorders.
- x. **Montgomery-Asberg Depression Rating (MADRS)** Scale used by clinicians to assess the severity of depression among patients who have a diagnosis of depression.
- xi. **Screen for Child Anxiety Related Disorders (SCARED)** Scale used by clinicians to assess the severity of anxiety in pediatric patients.
- xii. **Children’s Depression Rating Scale, Revised (CDRS-R)** Scale used for rating the severity of depression in pediatric patients

Table 3. Baseline procedures for all subjects and Follow-up procedures for UD subjects

[figure not shown]

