Questionnaires and Tools	Screening	Basel ine	Wk 2	Wk 4	2 mon	3 mon	Every mon from 4 - 6 months	Every 3 Months from 6 months – 24 Months
Diagnostic Instrument for Genetic Studies	X							
Kiddie Schedule for Affective Disorders and Schizophrenia								
DIGS/KSADS Mood Disorders Section	X							
SCID II	X							
Visual Analog Scale	X							
MINI International Neuropsychiatric Interview (MINI)	X	X	X	X	X	X	X	X
Childhood Events and Life Events Scales	X							
Physical Examination	X							
Clinical Psychiatric Interview	X							
Family Interview for Genetic Studies (FIGS) ⁸²	X							
Laboratory Tests:	X							
fMRI SCAN		X						
Genetic blood draw	X							
S100B , antibody, and cytokine testing	X							
Antidepressant Treatment		X	X	X	X	X	X	X
Hypomania Syndrome Checklist of schedule for Affective Disorders and Schizophrenia (HSC-SADS)	X	X	X	X	X	X	X	X
17-Item Hamilton Depression Scale (HDRS) ⁷⁹ - Children’s Depression Rating Scale (CDRS-R) Hamilton Anxiety Scale (HAM-A) Screen for Child Anxiety Related Disorders (Scared)	X	X	X	X	X	X	X	X
Montgomery-Asberg Depression Scale (MADRS)	X	X	X	X	X	X	X	X
Young Mania Rating Scale (YMRS) ⁷⁷	X	X	X	X	X	X	X	X

Columbia Suicide Severity Rating Scale (CSSRS)	X	X	X	X	X	X	X	X
Beck Scale for Suicide Ideation (BSSI)	X	X	X	X	X	X	X	X
Treatment Emergent Side Effects Scale (TESES)			X	X	X	X	X	X
Clinical Global Impression Scale – for Bipolar Disorder (CGI-BP) ⁸³	X	X	X	X	X	X	X	X

III. Rating for any episodes of subthreshold or over threshold (hypo)manic symptoms: At each follow-up time point the subject will be asked for any sustained periods since the last visit in which they felt more high, irritable or energetic than their normal self³. If the patient answers in the affirmative then they would be rated on the YMRS and MSC-SADS for that period as well as for DSM-IV criteria for conversion to BD.

2c(ii)H. fMRI Scan methodology: Subjects will be imaged using state-of-the-art whole-body 3T Siemens Trio-Tim MRI scanner. Before the imaging session, subjects will be trained regarding experimental procedures. The imaging session duration will be approximately 90 minutes.

Figure 7. Imaging session:

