E2b5. Worsening of symptoms before the baseline scan: Several steps will be taken for close monitoring of the patients during this study to prevent significant worsening of symptoms. First, we will not include patients with very severe symptoms as described above in E2b4, who are grossly disabled because of their mood symptoms or who have any significant suicidal ideation, intent or plan. Second, once the unmedicated patients are included in the study, they will be monitored closely with clinical visits every 3 days until the time that they have the first scan. Patients will be monitored at each visit with the (CSSRS). If patient's symptoms worsen, they will be monitored more frequently with the (CSSRS). They will be given emergency phone numbers with which they can contact either the principal investigator or a psychiatrist on the research team who will be available 24 hours, 7 days a week. If despite these interventions, at any time a patient's symptoms worsen by more than 10 points on the HAM-D or the YMRS, or significant worsening is judged by clinical evaluation e.g. suicidal ideation, the patient will be taken out of the study and treated clinically as necessary with pharmacotherapy and/or psychotherapy as an outpatient or hospitalized as an inpatient. An inpatient clinical as well as research unit is available at the participating hospitals to hospitalize patients if necessary. Patients will be followed up clinically as outpatients or inpatients until their condition is

improved and stabilized. At that point they will be referred to the clinician of their choice and referral will be arranged.

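### The 10-point HAM-D/YMRS withdrawal rule in E2b5 has no scheduled HAM-D or YMRS rating between screening and scan day

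*Combined protocol and SAP*

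**What the plan says.** Section E2b5 covers patients who are waiting, unmedicated, for the baseline scan. It sets "clinical visits every 3 days until the time that they have the first scan". On what is rated at those visits it says: "Patients will be monitored at each visit with the (CSSRS". If symptoms worsen, "they will be monitored more frequently with the (CSSRS" is the stated response.

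The same paragraph gives a withdrawal rule in two parts joined by an or. The numeric part applies if symptoms "worsen by more than 10 points on the HAM-D or the YMRS", with no restriction on when. The clinical part applies if "significant worsening is judged by clinical evaluation e.g. suicidal ideation".

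The rating-scale list in section 2c(ii)G describes the CSSRS as follows: "Scale used for identifying the presence and severity of suicide ideation". Section 2c(ii)E passes directly from Visit 1 (screening) to Visit 2 (scan day). The schedule, "Table 3. Baseline procedures for all subjects and Follow-up procedures for UD subjects", marks the HAM-D row and the "Young Mania Rating Scale (YMRS" row at Screening and at Baseline, with no column between them.

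**The concern.** A rule written in points on two scales works only if those scales are scored while the rule applies. Here it applies during the wait for the scan, and the one instrument assigned to that period measures something else. The escalation step does not help, because it calls for more of the same instrument.

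Section E1b5 lists severe depression, gross disability and becoming more manic among the risks of the waiting period and the study. UD patients are offered antidepressants only once the scan is done, and BDD patients are referred for treatment only after the baseline study (section 2c(ii)E). Manic worsening is the least well covered: the CSSRS does not measure it, and the clinical part of the rule gives suicidal ideation as its only example. What is at stake is one safeguard for the 160 planned patients (40 BDD and 120 UD).

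**Working it through.** The plan gives no figure to reproduce here. The check is a comparison of sections followed by a count.

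**Where HAM-D and YMRS are scheduled before treatment**

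- Section 2c(ii)E, Visit 1: both scales, with the CDRS-R offered as the alternative to the HAM-D.
- Section E2b5, visits every 3 days: the CSSRS is the only instrument named.
- Section 2c(ii)E, Visit 2: mood questionnaires on the same day as the scan. Table 3 marks both scales in the Baseline column, which is also the scan column.
- Sections E1b4, E1b5, E2b4 and E2b6 to E2b11: no interim HAM-D or YMRS.

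Scheduled HAM-D or YMRS ratings between screening and scan day: 0.

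**Scores that would meet the numeric part**

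A worsening of more than 10 points means at least 11. Entry limits are from section E1a.

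- HAM-D above 15 and below 25 is 16 to 24 at entry. Trigger score: 16 + 11 = 27 to 24 + 11 = 35.
- YMRS below 10 is 0 to 9 at entry. Trigger score: 0 + 11 = 11 to 9 + 11 = 20.

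**Interim visits, gaps and workload**

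Day 0 is inclusion, with the screening ratings assumed to be taken then. Visits fall on days 3, 6, 9 and so on, and only those before scan day are counted. The longest gap between scheduled ratings is now the whole wait; with both scales at each interim visit it is at most 3 days. Extra ratings per patient = 2 scales × interim visits; the total multiplies this by 160.

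| Wait (days) | Interim visits | Longest gap now (days) | Longest gap with fix (days) | Extra ratings per patient | Total for 160 |
|---|---|---|---|---|---|
| 3 | 0 | 3 | 3 | 0 | 0 |
| 5 | 1 | 5 | 3 | 2 | 320 |
| 7 | 2 | 7 | 3 | 4 | 640 |
| 10 | 3 | 10 | 3 | 6 | 960 |
| 14 | 4 | 14 | 3 | 8 | 1,280 |
| 21 | 6 | 21 | 3 | 12 | 1,920 |

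**Which rows apply**

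Section E2b4 reports that the scan is usually arranged inside a week, so the rows up to 7 days are the usual case. Its 7 to 10 days describes ordinary clinical evaluation periods and how long a patient must be able to tolerate being off medication; it is not the expected wait. The 14 and 21 day rows apply only if the few weeks of possible treatment delay in section E1b4 are assumed to mean 14 to 21 days.

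**The case against.** The strongest reply is that silence is not exclusion. E2b5 orders clinical visits and adds the CSSRS in a separate sentence, without saying that nothing else is rated. A rule stated in HAM-D and YMRS points may be taken to imply that staff will obtain those scores when they suspect worsening. The clinical part covers any significant worsening, since suicidal ideation is only its example. The patients enter with limited severity, are seen every 3 days and can reach a psychiatrist at any hour. On this view the gap is one of wording, and rating on suspicion would be enough.

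Much of this stands, and it rules out three stronger readings. A reader might infer that patients are unmonitored for depression or mania before the scan. They are not, because the clinical part operates at every visit. A reader might infer that the plan forbids interim HAM-D or YMRS ratings. It does not; the CSSRS is the only instrument named, not the only one permitted. A reader might take 7 to 10 days or longer as the routine gap. E2b4 does not support that.

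What does not stand is the step from implied to sufficient. If the scales are given only when a clinician already suspects worsening, the numeric part depends on the judgement it was meant to supplement. Followed as written, the schedule supplies no score for it, and the instrument it does supply cannot stand in.

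**Conclusion.** The point holds as a narrow safety gap. The numeric part of the E2b5 rule is first checked by schedule on scan day, at the end of the period it is meant to protect. In the usual case this affects 0 to 2 interim visits and leaves up to 7 days between ratings. For a 7 to 10 day wait it is 2 to 3 visits; for an assumed 14 to 21 day wait, 4 to 6.

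The visit counts rest on exact 3-day spacing and on screening ratings taken at inclusion. The documents do not allow an estimate of how many patients would cross the threshold, or of how many clinical judgement would miss, so no claim of expected harm is made.

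A reader might also infer damage to the study's results. Nothing supports that: no aim, endpoint, sample size or analysis is affected. This is a cheap improvement and a minor safety fix.

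**What to change.** In E2b5 and in the visit schedule (section 2c(ii)E, with a pre-scan column in Table 3), add the HAM-D and YMRS to each 3-day visit before the scan, alongside the CSSRS. State that change is counted from the screening score. Use the HAM-D for minors too: the schedule allows the CDRS-R as an alternative, but eligibility in E1a and the withdrawal rule are both written in HAM-D points. Leave the 10-point threshold and the clinical part as they are.

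The cost is protocol and case report form wording, plus rating time by staff already trained on these scales, at visits already planned. That is about 0 to 4 extra ratings per patient in the usual case (0 to 640 over 160 patients), or 4 to 6 for a 7 to 10 day wait (640 to 960). Rating only on suspicion would cost less and would be better than the present text, but would still leave the numeric part without a check of its own.
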